### 6.5.5. Laboratory Evaluations

Post-baseline laboratory assessments less than the lower limit of detection (i.e., < LLD) are imputed as LLD/2. If no LLD is available, then the imputed value is the minimum numeric value listed divided by 2 (e.g., < 25 is 25/2=12.5). Laboratory assessments above the ULD are imputed as the ULD. If the lab result is qualitative but presented as > X and X is 10 times greater than the ULN, then the value X is used in the analysis.

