#### **4.5. Clinical Assessments**

All patients in the study follow the same visit and assessment schedule for the 2 years of total follow-up. [Table 2](#) lists the overall schedule of assessments for the study. Following the first dose of study drug on Day 1, patients are scheduled for in-person assessments during Year 1 of treatment at Weeks 1, 2, 4, 6, 8, 12, 24, 36, and 48, as well as by telephone contact on Days 3, 10, 21, 31, 38, and 45. Patients temporarily discontinue study treatment at Week 48 and are assessed at an in-person Year 1 follow-up visit at Week 52 (4 weeks after the last dose). Patients are dispensed treatment at the end of their Week 52 visit at the same dose level (or matching placebo) as the last dose at Week 48. Patients are assessed for in-person assessments during Year 2 of treatment Weeks 64, 76, 88, and 100. Patients are assessed at an in-person, Year 2 follow-up visit at Week 104 (4 weeks after the last dose).

Assessment	Screen A a	Screen B b	Day 1 c	Wk 1 (Phone) Day 3±2	Wk 1 Day 7±3	Wk 2 (Phone) Day 10±2	Wk 2 Day 14±3	Wk 3 (Phone) Day 21±2	Wk 4 Day 28±3	Wk 4 (Phone) Day 31±2	Wk 5 (Phone) Day 38±2	Wk 6 Day 42±3	Wk 7 (Phone) Day 45±2	Wk 8 Day 50±3	Wk 12 Day 84±3
Informed consent	X														
Inclusion/ exclusion	X		X d												
Demographics and baseline disease characteristics	X														
Concomitant medications	X	X	X	X	X	X	X	X	X	X	X	X	X	X	X
Medical history	X														
Height	X		X	X	X	X	X	X	X	X	X	X	X	X	X
Weight in clinic	X		X	X	X	X	X	X	X	X	X	X	X	X	X
Weight at home			X	X	X	X	X	X	X	X	X	X	X	X	X
Dispense weight diary			X	X	X	X	X	X	X	X	X	X	X	X	X
Collect/review weight diary				X	X	X	X	X	X	X	X	X	X	X	X
ECG	X														
Echocardiogram e	X														
Vital sign measurements	X		X	X	X	X	X	X	X	X	X	X	X	X	X
Physical exam	X		X	X	X	X	X	X	X	X	X	X	X	X	X
Pregnancy test for WOCBP f	X	X	X	X	X	X	X	X	X	X	X	X	X	X	X
Study drug administration															
Dispense study drug			X				X		X			X		X	X
Collect study drug							X		X			X		X	X
Telephone contact				X		X		X		X	X		X		
Adverse event collection			X g	X	X	X	X	X	X	X	X	X	X	X	X
Genetic testing h	X														
Clinical chemistry (incl. eGFR)	X	X	X	X	X	X	X	X	X	X	X	X	X	X	X
BNP and NT-proBNP	X		X	X	X	X	X	X	X	X	X	X	X	X	X
IGF-1 and serum ketones	X		X	X	X	X	X	X	X	X	X	X	X	X	X
Hemoglobin A1c	X														
Hematology	X		X	X	X	X	X	X	X	X	X	X	X	X	X
Urinalysis and microscopy	X		X	X	X	X	X	X	X	X	X	X	X	X	X

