## **6. GENERAL CONSIDERATIONS FOR DATA ANALYSES AND HANDLING**

The efficacy and safety analyses use the analysis sets defined in Section 6.3. Patient listings (as appropriate) of all analysis data that support summary tables and/or figures are provided along with their source data. The summary tables do not include measurements from patients excluded from the pre-defined analysis sets or extra measurements (such as unscheduled or repeat assessments) not closest to the target study day unless specified otherwise, but the patient listings do include these data. Missing data are not imputed, unless otherwise specified. In general, patient listings are sorted by patient number and assessment date (time and parameter, as applicable). Any laboratory value (including eGFR), vital sign assessment, or ECG value collected after starting dialysis or after receiving a kidney transplant is considered invalid and will be treated as missing.

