### **6.4.3. Safety Assessments**

Baseline for continuous safety assessments (i.e., vital sign assessments, weight, BMI, and laboratory measurements) is defined as the average value of measurements collected up through the date of, but not after, first study drug administration.

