### 6.5.7. Urine Albumin to Creatinine Ratio (ACR)

ACR is provided in the central laboratory database as the ratio of urine albumin to urine creatinine from the first morning void (FMV) urine collection. The ACR value is reported in the central laboratory database as missing when the FMV urine albumin result is < LLD. Urine albumin results < LLD and the corresponding ACR missing values are imputed as follows:

- If urine albumin result = < LLD, then
  - Imputed urine albumin result (mg/dL) = LLD/2
  - Imputed ACR(mg/g) = (imputed urine albumin result in mg/dL) / [(urine creatinine in mg/dL) /1000]

The ACR results are log-transformed for analysis to produce data that are more normally distributed. Any imputed ACR result where ACR=0 is considered to be 0.1 mg/g for purposes of calculating the geometric mean.

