#### **10.5.1. Continuous Summaries of Laboratory Results**

Selected laboratory evaluations and change from baseline are summarized by treatment, laboratory category (hematology, chemistry), test, and study visit using continuous statistics. The estimated glomerular filtration rate (eGFR) results are calculated using formulas described in Section 6.5.6.

The change from baseline in select laboratory evaluations at protocol endpoint time points (i.e., Week 48, 52, 100, and 104) for patients treated with bardoxolone methyl compared to placebo may be performed using the analysis of covariance (ANCOVA) model described in Section 8.7.1 and Section 8.9.1 .

Box plots and line graphs are generated for selected laboratory test results, such as eGFR, ACR, alanine aminotransferase (ALT), aspartate aminotransferase (AST), total bilirubin, BNP, BUN, uric acid, magnesium, creatinine, and creatine kinase (CK). Line graphs include mean  $\pm$  SE over time for both the observed values and for change from baseline.

Due to the nature of urinalysis parameters, summaries of continuous statistics are not provided unless otherwise specified. The one exception is the urine albumin to creatinine ratio (ACR) from the first morning void urine collection. Qualitative lab results, including urinalysis, are included in the listings, but are not summarized. Laboratory results that are above or below normal limits are flagged in the listings.

Summaries of ACR (Section 6.5.7) will use the geometric mean with 95% confidence intervals instead of the arithmetic mean and will display ACR results in original units of mg/g. Changes from baseline in ACR are reported as the post-baseline/baseline ratios and are summarized by geometric means with 95% confidence intervals at each time point. Summaries of ACR will use the geometric mean instead of the arithmetic mean. Presentations will display ACR results in the original units (mg/g). Changes in ACR are calculated as the ratio of each visit to baseline. Similar ANCOVA analyses as described in this section will be performed for ACR ratio to baseline.

Additionally, ACR is summarized by baseline ACR quartile. Descriptive summaries at each visit include the standard deviation, geometric mean of ACR, as well as the geometric mean of % change from baseline. Summaries of ACR exclude values within the Week 2 and Week 6 visit windows.

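### SAP 6.5.5 substitutes LLD/2 only after baseline, so pre-dose results below the detection limit have no stated value and laboratory change from baseline treats its two sides differently (minor)

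*SAP*

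**What the plan says.** Section 6.5.5 (Laboratory Evaluations) gives the general rule: "Post-baseline laboratory assessments less than the lower limit of detection (i.e., < LLD) are imputed as LLD/2". The fallback when no limit is known is "If no LLD is available, then the imputed value is the minimum numeric value listed divided by 2 (e.g., < 25 is 25/2=12.5". The upper-limit rule in the same paragraph carries no time restriction: "Laboratory assessments above the ULD are imputed as the ULD".

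For continuous safety assessments, laboratory tests included, Section 6.4.3 says that baseline "is defined as the average value of measurements collected up through the date of, but not after, first study drug administration". It does not say what to do with a result reported only as below the limit. Section 6 sets the default: "Missing data are not imputed, unless otherwise specified".

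ACR is handled separately. Section 6.5.7 says "Urine albumin results < LLD and the corresponding ACR missing values are imputed as follows", with no restriction to post-baseline samples.

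The use of these baselines is set out in Section 10.5.1: "Selected laboratory evaluations and change from baseline are summarized by treatment, laboratory category (hematology, chemistry), test, and study visit using continuous statistics". That section also plans graphs of change from baseline for selected tests, names BNP among them, and allows an optional ANCOVA on change. In the schedule of assessments (Section 4.5, Table 2), the row "BNP and NT-proBNP" has two pre-dose samples, Screen A and Day 1.

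**The concern.** Change from baseline needs the same measurement rule on both sides of the subtraction. Here an undetectable result after dosing becomes LLD/2, while the same result before dosing has no stated value. If it is treated as non-numeric, two things happen:

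- A patient whose pre-dose results are all below the limit has no baseline and leaves every change-from-baseline display for that test.
- A patient with one detectable and one undetectable pre-dose result gets a baseline equal to the detectable one, which is too high.

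Patients with the lowest starting values would then be lost or misplaced in safety summaries meant to show whether a marker moves on treatment. The ULD and ACR rules have no such restriction, so it belongs to this one sentence.

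**Working it through.** **1. The plan's own figure.** The worked example in 6.5.5 is a result of <25 analysed as 25/2 = 12.5. It reproduces. The rule feeds no sample size, power or alpha calculation.

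**2. Coverage of a pre-dose result below LLD.**

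| SAP section | Applies to | Covers a non-ACR baseline below LLD? |
|---|---|---|
| 6.5.5, LLD rule | post-baseline results | no |
| 6.5.5, ULD rule | results above the upper limit, any time | no |
| 6.5.7 | ACR, any time | no |
| 6.4.3 | average of pre-dose values | no rule given |
| 6 | missing data | not imputed unless specified |

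No section supplies the number.

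**3. One patient.** Take LLD = 10, pre-dose results <10 and 14, post-dose 14.

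- Literal: baseline 14, change 14 - 14 = 0.
- LLD/2 throughout: baseline (5 + 14)/2 = 9.5, change 14 - 9.5 = +4.5.

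In general, with one detectable value D and one undetectable value, the literal baseline exceeds the consistent one by D - (D + LLD/2)/2 = (D - LLD/2)/2. This is always positive because D is at least LLD. For such patients the shift in change is therefore always downward.

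**4. Group means, first set of assumptions.** The documents give no detection limit, distribution or share below the limit, so everything here is assumed. The analyte is lognormal with between-patient log SD 0.6 and within-patient log SD 0.4. There are two pre-dose values and one post-dose value, LLD is 10, and any rise is proportional. Entries are mean change, literal / LLD/2 throughout, and are good to about 0.1.

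| Median | Baselines lost | No true change | 40% rise | Doubling |
|---|---|---|---|---|
| 8 | 50% | -3.4 / 0.0 | not tabulated | +11.7 / +10.3 |
| 12 | 28% | -2.4 / 0.0 | +5.3 / +6.4 | +16.7 / +15.9 |
| 20 | 9% | -1.3 / 0.0 | not tabulated | +26.6 / +26.2 |

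Between arms at median 12, with a 40% rise in one arm and none in the other:

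- Literal: 5.3 - (-2.4) = 7.7.
- Consistent: 6.4 - 0.0 = 6.4.
- Ratio: 7.7/6.4 = 1.20.

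**5. Second set of assumptions.** Total log SD is 0.8, within-patient correlation 0.6 to 0.8, and 10%, 30% or 50% of pre-dose values lie below LLD = 10.

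- Baselines lost: 4% to 40%. A further 9% to 30% of patients have a baseline from the detectable value alone, with a mean shift of -4.6 to -7.7 in those patients.
- No true change: literal mean change -0.6 to -3.8, against -0.04 to +0.02 with LLD/2 throughout.
- Rise x1.5, literal minus consistent: -0.6 to -1.8 at correlation 0.6, but +0.3 to +0.7 at 0.8.
- Rise x2.0, literal minus consistent: about 0 at correlation 0.6, and +1.1 to +3.2 at 0.8.
- Between arms at correlation 0.7: no distortion when neither arm changes. With x1.5 in one arm only, 20.0 against 19.3, 12.3 against 10.7, and 9.3 against 6.9 (10%, 30%, 50% below LLD).

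**6. Why the sign turns.** With no true change, the patients who lose their baseline would have had the higher mean change (+1.1 to +5.4, against -0.2 to -1.2 in those kept), so losing them lowers the mean. With a doubling they have the smaller absolute rise (+6.6 to +16.7, against +16.6 to +40.2), so losing them raises it. Between randomized arms the too-high baselines cancel. What remains is that the patients kept start higher and so show a larger absolute response to a proportional effect.

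**The case against.** The strongest reply is that the loss of baselines is inferred from silence. The Section 6 default concerns missing data, and a result reported as below the limit has been reported. Only for ACR does the SAP say that the laboratory database returns a missing value, and there it supplies a rule. Section 8 also refers further detail of the statistical approach to a programming conventions document that is not among the papers. All this stands to the extent that dropping such values is the literal reading of three sections together, not an express instruction. It does not close the gap: a programmer who applied LLD/2 to a baseline would be going beyond the written rule.

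Three stronger readings are tempting, and the documents do not support them.

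- **A reader might infer a general downward bias that hides a rise.** Steps 4 to 6 show otherwise. The within-arm error can reverse with a large rise, and the treatment contrast is overstated, not hidden, when only one arm rises.
- **A reader might infer that BNP baselines in particular are lost.** The SAP gives no BNP or NT-proBNP detection limit and no share of patients near it. BNP fits structurally, with two pre-dose samples and graphs of change, but it is only a possible example.
- **A reader might cite the BNP > 200 pg/mL count in Section 10.5.2.** That count does not use baseline.

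The limited reach is also fairly raised. Section 10 makes safety descriptive without formal testing, the laboratory ANCOVA is optional, and patients without a baseline still appear in the planned graphs of observed values.

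**Conclusion.** The point holds as a minor defect. As written, the SAP gives an undetectable result a value after dosing and none before it, for every test except ACR. If followed literally, change-from-baseline summaries are distorted for any test with results below LLD. Within an arm the distortion is usually downward when true change is small and possibly upward when the rise is large. Between arms there is none when neither arm changes, and an overstatement when one arm has a proportional rise and the other does not.

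The sizes above rest on assumed lognormal distributions, an arbitrary LLD of 10 units and assumed shares below it. Which tests are affected, and by how much, cannot be determined from the documents. If no pre-dose result falls below LLD, the effect is nil.

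The eGFR endpoints have their own baseline (6.4.1) and are not affected. ACR, the BNP > 200 pg/mL count, alpha and power are likewise outside the problem.

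**What to change.** Delete the opening qualifier (Post-baseline) in 6.5.5, so that every result below LLD is set to LLD/2 before the baseline in 6.4.3 is averaged and change is computed. A cross-reference in 6.4.3 would serve the same end. Report, by test and arm, how many baselines contain an imputed value.

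The cost is one word, one added count and no new data, with one reservation. Section 5.1.1 treats results through Week 52 as final once Year 1 data are complete. If those tables already exist, the affected Year 1 laboratory tables should be re-run, or a footnote should state that Year 1 and Year 2 baselines differ for the tests concerned.

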### 6.5.6. Estimated Glomerular Filtration Rate (eGFR)

The eGFR is calculated using the formula below according to patient's age at the date of consent. The formula will not change throughout the study. The Chronic Kidney Disease Epidemiology Collaboration (CKD-EPI) equation is used for adult patients (age at consent at least 18 years):

- $eGFR \text{ (mL/min/1.73 m}^2\text{)} = 141 \times \min(S_{cr}/\kappa, 1)^\alpha \times \max(S_{cr}/\kappa, 1)^{-1.209} \times 0.993^{\text{Age}} \times 1.018 \text{ [if female]} \times 1.159 \text{ [if black]}$

The Bedside Schwartz equation is used for pediatric patients (age at consent of 12 to 17):

- $eGFR \text{ (mL/min/1.73 m}^2\text{)} = (0.41 \times \text{Height in cm}) / S_{cr}$

where  $S_{cr}$  is serum creatinine (mg/dL),  $\kappa$  is 0.7 for females or 0.9 for males, and  $\alpha$  is -0.329 for females or -0.411 for males. Min indicates the minimum of  $S_{cr}/\kappa$  and 1, and max indicates the maximum of  $S_{cr}/\kappa$  and 1. *Age* indicates age at time of serum creatinine collection. *Height* indicates height at time of serum creatinine collection.

### 6.5.6.1. Prognosis of CKD by eGFR and Albuminuria Category

Prognosis of CKD is determined by the intersection of the following eGFR and albuminuria categories (KDIGO 2012):

**Table 5. eGFR Category**

eGFR Category	eGFR (mL/min/1.73 m  )
1	≥ 90
2	60 to < 90
3a	45 to < 60
3b	30 to < 45
4	15 to < 30
5	< 15

**Table 6. Albuminuria Category**

ACR Category	ACR (mg/g)
1	< 30
2	30 to ≤ 300
3	> 300

### 6.5.7. Urine Albumin to Creatinine Ratio (ACR)

ACR is provided in the central laboratory database as the ratio of urine albumin to urine creatinine from the first morning void (FMV) urine collection. The ACR value is reported in the central laboratory database as missing when the FMV urine albumin result is < LLD. Urine albumin results < LLD and the corresponding ACR missing values are imputed as follows:

- If urine albumin result = < LLD, then
  - Imputed urine albumin result (mg/dL) = LLD/2
  - Imputed ACR(mg/g) = (imputed urine albumin result in mg/dL) / [(urine creatinine in mg/dL) /1000]

The ACR results are log-transformed for analysis to produce data that are more normally distributed. Any imputed ACR result where ACR=0 is considered to be 0.1 mg/g for purposes of calculating the geometric mean.

#### **6.5.7.1. Baseline Urine Albumin to Creatinine Ratio (ACR) Categorical Status**

Baseline ACR status will also be grouped by the following categories using baseline ACR:

- < 30 mg/g
- 30 mg/g < ACR <= 300 mg/g
- 300 mg/g < ACR <= 1000 mg/g
- 1000 mg/g < ACR <= 3500 mg/g
- ACR > 3500 mg/g

#### **6.5.7.2. ACR Category used in Stratification (ACR\_STRAT)**

The ACR category used for stratification (ACR\_STRAT) is determined by the randomization list with the following categories:

- ACR <= 300 mg/g
- 300 mg < ACR <= 1000 mg/g
- 1000 mg/g < ACR <=3500mg/g

#### **6.5.8. Electrocardiogram Fridericia Corrected QT Interval**

Electrocardiogram intervals are assessed locally at each site. The following formula is used to calculate the QTcF interval for analysis from QT and RR intervals:

- $QTcF = QT / \sqrt[3]{RR}$

where RR = 60 / (Heart Rate).

#### **6.5.9. Log of The Minimum Angle of Resolution**

Best-corrected visual acuity (BCVA) assessments are performed at time points specified in the scheduled assessments in [Table 2](#). The Snellen chart values are used to derive the log of the minimum angle of resolution (logMAR) value as below:

- LogMAR = - log10 (Snellen)

#### **6.5.10. Natural log(ACR)/eGFR**

To evaluate ACR after adjusting for filtration rate, ln(ACR)/eGFR (Sections [6.5.7](#) and [6.5.6](#)) is assessed.

#### **6.5.11. Exposure Duration**

Exposure duration is used in analysis of efficacy to adjust analysis of off-treatment eGFR for the exposure duration within each year. Fraction of expected exposure duration is calculated for the first and second years of treatment as follows:

- First year exposure (TRT\_EXP1) =  
[(date of last dose in first year) – (date of first dose)]/336
- Second year exposure (TRT\_EXP2) =  
[(date of last dose in second year) – (date of first dose)]/700

where 336 is the number of days in the first year (i.e., 48-week) treatment interval, and 700 is the number of days in the second year (i.e., 100-week) treatment interval. Exposure in the second year is simply total exposure and does not subtract the 4-week off-treatment period at the end of the first year.

## **6.6. Handling of Missing Data**

### **6.6.1. Missing Efficacy Endpoint Data**

The primary analysis of efficacy is based on an assumption of missing at random (MAR) (Section 8.5). The tipping point sensitivity analysis (Section 8.6.2.1) is performed to assess how severe departures from MAR must be in order to overturn conclusions from the primary analysis.

#### **6.6.1.1. Missing eGFR for MMRM Analyses**

Missing eGFR data are not imputed for the primary MMRM analysis of the primary endpoints (Week 48 and Week 100). A set of sensitivity analyses is included to assess the robustness of conclusions to the MAR assumption (see Section 8.6.2 and Section 8.8.2) for the primary analysis of the primary endpoints (Week 48 and Week 100).

#### **6.6.1.2. Missing eGFR for ANCOVA Analyses**

Missing eGFR data are imputed for the primary ANCOVA analysis of the key secondary endpoints (Week 52 and Week 104) using multiple imputation based on an assumption of MAR. A set of sensitivity analyses is included to assess the robustness of conclusions to the MAR assumption (see Section 8.7.2 and Section 8.9.2) for the primary analysis of the key secondary endpoints (Week 52 and Week 104).

### **6.6.2. Missing Start and Stop Dates for Concomitant Medication**

Missing start dates for concomitant medications are not imputed.

Concomitant medications with incomplete end dates are considered concomitant medications if:

- Day and month are missing, and the year is equal to or after the year of the first date of study drug administration;
- Day is missing and the year is after the year of the first date of study drug administration;
- Day is missing and the year is equal to the year of the first date of study drug administration and the month is equal to or after the month of the first date of study drug administration; or
- Year is missing.

### **6.6.3. Missing Start and Stop Dates for Adverse Events**

Treatment-emergent adverse events (TEAEs) are events that either:

- Have a date of onset on or after the date of the first dose and not more than 30 days after the date of the last dose of study drug, or
- Have no recorded date of onset with a stop date after the first dose of study drug, or
- Have no recorded date of onset or stop date.

Adverse events with incomplete start dates are considered after the date of first dose if:

- Day and month are missing and the year is equal to or after the year of the first date of study drug dosing;
- Day is missing and the year is after the year of the first date of study drug dosing;
- Day is missing and the year is equal to the year of the first date of study drug dosing and the month is equal to or after the month of the first date of study drug dosing; or
- Year is missing.

Adverse events with incomplete start dates are considered on or within 30 days of last dose, if:

- Day and month are missing and the year is equal to or before the year of the date of last dose of study drug plus 30 days;
- Day is missing and the year is equal to or before the year of the date of last dose of study drug plus 30 days and month is equal to or before the month of the date of last dose of study drug plus 30 days;
- Year is missing.

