### 10.1. Adverse Event Preferred Term and Body/Organ System Summary Tables

AEs are summarized by treatment as defined by the safety analysis set. In addition to being summarized by treatment year, AEs are also summarized overall. General considerations for AE summaries and calculations are:

- Multiple events by preferred term (PT) and system organ class (SOC) are counted once only per patient for summaries of AE incidence.
- For summaries of AE incidence by severity, only the most severe event is counted per patient.
- For summaries of AE incidence by relationship, only the most related event is counted per patient.
- An AE with a missing resolution date or incomplete date that is not identified as continuing is assumed to be continuing and no duration is calculated.
- Treatment-emergent adverse events (TEAEs) are summarized separately from off-treatment adverse events (OTAEs).
- For summaries of the number of AE events, all AEs are counted.

AEs are coded using MedDRA (Medical Dictionary for Regulatory Activities) version 19.1. In MedDRA, each verbatim term is mapped to a preferred term and high level term (HLT), which is then mapped to a system organ class. Tables and listings will present data at the SOC and PT level.

Treatment-emergent adverse events (TEAEs) are events that either:

- Have a date of onset on or after the date of the date of first dose and not more than 30 days after the date of the last dose of study drug, or
- Have no recorded date of onset with a stop date after the first dose of study drug, or
- Have no recorded date of onset or stop date

AEs with an onset greater than 30 days after the last dose of study drug, and therefore not treatment-emergent AEs (TEAEs), are classified as off-treatment AEs (OTAEs). Analyses described for TEAEs are also performed for OTAEs and tabulated separately.

The investigator grades the severity of the AEs as mild, moderate, or severe as defined in the study protocol. The investigators graded association or relatedness to the study medication according to criteria specified in Section 11.4 of the study protocol.

As defined in the protocol, a serious adverse event (SAE) is an adverse event that results in any of the following:

- Death;
- A life-threatening adverse drug experience;
- Inpatient hospitalization or prolongation of existing hospitalization;
- Results in persistent or significant incapacity or substantial disruption of the ability to conduct normal life functions;

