#### **10.1.1. Missing and Partial AE Onset Dates**

Rules for handling missing or partial AE Onset Dates are included in Section 6.6.3.

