#### **10.1.2. Summaries of Adverse Events**

TEAEs and OTAEs are summarized by treatment based on year of AE onset, and overall. For each treatment, SOC, and PT, the number and percentage of patients reporting an event is calculated. In summary tables, SOC is presented alphabetically and events within SOC are presented by decreasing frequency count.

Summary tables (number and percentage of patients and events) of AEs (by SOC and PT) are provided by treatment as follows:

- All treatment-emergent AEs
- All treatment-emergent related AEs (definitely, probably, or possibly related)
- All treatment-emergent AEs by severity
- All treatment-emergent serious adverse events (including deaths)
- All related treatment-emergent serious adverse events (including deaths)
- All treatment-emergent adverse events leading to permanent discontinuation of study drug

Listings are provided showing:

- All AEs
- Serious adverse events (including deaths)

- AEs leading to permanent discontinuation of study drug

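### SAP 6.6.3: the rule for adverse events with a missing onset day compares month numbers across different years, so some events that began on treatment fail the treatment-emergent test

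*SAP*

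**What the plan says.** SAP 6.6.3 and 10.1 define a treatment-emergent adverse event (TEAE) as one with onset from first dose to 30 days after last dose. Later events are off-treatment events (OTAEs), which 10.1 describes as "AEs with an onset greater than 30 days after the last dose of study drug, and therefore not treatment-emergent AEs". For incomplete dates, 10.1.1 gives no rule of its own: "Rules for handling missing or partial AE Onset Dates are included in Section 6.6.3".

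Section 6.6.3 then has two lists. One decides whether the event began after first dose. The other decides whether it began on or within 30 days of last dose. The second list has three bullets:

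- Day and month missing, which tests the year alone: "Day and month are missing and the year is equal to or before the year of the date of last dose" plus 30 days.
- Day missing. The year must be equal to or before the cutoff year, "and month is equal to or before the month of the date of last dose of study drug plus 30 days".
- Year missing.

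The first-dose list treats a missing day differently. A later year passes with no month test ("Day is missing and the year is after the year of the first date of study drug dosing"), and the month is compared only when the years are equal. The concomitant-medication list in 6.6.2 is split in the same way ("Day is missing and the year is after the year of the first date of study drug administration"). The SAP addendum does not alter the 6.6.3 bullet.

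**The concern.** A month number can be compared with the cutoff month only if both belong to the same year. The bullet applies the comparison to every earlier year as well. An event from late in one calendar year therefore fails when the cutoff falls early in the next, although the whole month lies before last dose.

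Treatment lasts 100 weeks, so every completer's exposure crosses at least one year-end. Safety assessments are listed among the primary endpoints for each year (SAP 3.1.1.1 and 3.1.2.1). TEAE status decides which events enter the main tables in 10.1.2: all, related, by severity, serious, and leading to discontinuation. That section says "TEAEs and OTAEs are summarized by treatment based on year of AE onset, and overall", so an event that fails the bullet drops out of the TEAE tables and by implication goes to the OTAE tables. The SAP does not state that move; it is inferred from the failed test.

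**Working it through.** The SAP gives no figure for this rule, so the check is of its logic, with a count of the dates affected.

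**The rules.** Let the cutoff be last dose + 30 days, with year Yc and month Mc. Let the onset have known year Y and month M, with the day missing.

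- As written: pass if Y ≤ Yc and M ≤ Mc.
- Split by year, as in the first-dose list: pass if Y < Yc, or if Y = Yc and M ≤ Mc.

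Any date that passes as written also passes the split rule, so an error can only go one way: too few TEAEs.

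**Worked example (assumed dates).** First dose is 15 February 2018. Counting both ends, 700 days of treatment gives last dose on 15 January 2020. Adding 30 days gives a cutoff of 14 February 2020, so Yc = 2020 and Mc = 2.

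| Onset as recorded | Test in 6.6.3 | Result |
|---|---|---|
| November 2019 | 2019 ≤ 2020 holds; 11 ≤ 2 does not | fails |
| 2019 only | 2019 ≤ 2020 holds | passes |

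Neither other bullet rescues the first record, because its month and year are both known. Knowing more about the date turns a pass into a fail. Every day of November 2019 lies between first and last dose, so the event meets the main TEAE definition and cannot meet the OTAE definition. In this example March to December 2018 (10 months) and March to December 2019 (10 months) fail: 20 of the 24 calendar months of treatment.

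**Share of onset months that fail.** Take the S calendar months ending at the cutoff month. For S = 24, the year before the cutoff year contributes 12 − Mc failing months and the year before that another 12 − Mc, giving 2 × (12 − Mc). January gives 22/24, June 12/24 and December 0/24. Summed over the 12 cutoff months this is 2 × 66 = 132 of 288.

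| Span S | Failing months, all 12 cutoff months | Share |
|---|---|---|
| 3 months | 3/36 | 8.3% |
| 6 months | 15/72 | 20.8% (zero for June to December cutoffs) |
| 12 months | 66/144 | 45.8% |
| 24 months | 132/288 | 45.8% |

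**Day-level check.** This takes 700 days of treatment, last dose on each date of 2019 and 2020 (assumed), and onset on each day from first dose to last dose + 30. The mean share failing is 45.9%, range 0% to 91.6%. Counting only days up to last dose, with first dose on each date of 2017 to 2020 (assumed), the mean is 48%, range 0% to 96%. On that second base about 92% of first-dose dates have at least one failing day.

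**Split rule.** None of the 288 months fails. No on-treatment day fails for any first-dose date tried, with 84, 336, 700 or 707 days of exposure.

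**The case against.** The strongest reply is that the list only resolves ambiguous dates. Its bullets can be read as sufficient conditions, and an onset in November 2019 with last dose in January 2020 is not ambiguous: the main definition already makes it treatment-emergent. The intended rule can also be seen from the first-dose and medication lists, and a careful programmer may apply it. This is a fair account of the intent, but it does not repair the text. Section 10.1.1 sends incomplete dates to 6.6.3, and reading its list as complete is natural. Two programmers could then produce different tables from the same plan.

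The second reply concerns size. An event is affected only if its day is missing, its month and year are known, its year is before the cutoff year, and its month number exceeds the cutoff month. The SAP schedules frequent contacts in Year 1, so missing days may be uncommon, although Year 2 visits are about 12 weeks apart. This stands: the percentages describe the rule and do not predict misclassified events.

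The third reply is that the stakes are limited. Safety is summarised without formal testing, no efficacy result depends on the bullet, and the rule does not refer to treatment arm. For OTAEs, "Analyses described for TEAEs are also performed for OTAEs and tabulated separately", and all events, serious events and events leading to discontinuation are listed. This also stands, and it limits the importance of the error.

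**Conclusion.** The bullet is wrong as written. Followed literally, it fails some events that began on treatment, and it contradicts the TEAE and OTAE definitions that it is meant to apply. The logical error does not depend on any assumption beyond a missing day, an earlier year and a higher month number.

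The size does depend on assumptions. With evenly spread onset and cutoff months, 45.8% of possible onset months fail over a 12- or 24-month span, and fewer over shorter spans. The share is zero for a December cutoff, or when first dose to cutoff lies within one calendar year. The documents do not give the number of events with a missing day, nor whether any serious or related events are among them, so the effect on the tables is unknown. The risk is an under-count of TEAEs. It does not threaten the efficacy conclusions, and no safety data are lost.

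**What to change.** Replace the single day-missing bullet in SAP 6.6.3 with two, where the cutoff is the date of last dose plus 30 days:

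- the onset day is missing and the onset year is earlier than the cutoff year; or
- the onset day is missing, the onset year is the cutoff year, and the onset month is no later than the cutoff month.

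Check that the derivation program follows the corrected rule. As an optional addition, give the number of adverse events with a missing onset day by arm in a table footnote, so that the reader can see how many depend on the rule.

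The cost is one bullet in the SAP, one line of code and, if the count is added, one footnote. No new data are needed.
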